Chronic pain is accompanied by a host of emotional, behavioral, and cognitive psychosocial consequences. At the same time, psychosocial factors contribute to chronic pain, including fear of movement and catastrophizing, maladaptive emotional and cognitive processes, and adverse life experiences. Treatment guidelines stress the importance of psychosocial aspects in pain management. Unfortunately, both patients and medical providers find it difficult to discuss psychosocial problems. The goal of this project is to remedy this critical problem by developing and pilot testing novel therapeutic interviews delivered by next-generation Virtual Humans (VHs) to help patients engage in discussions about pain-related psychosocial factors. In this IRB application, we will develop VH-assisted therapeutic psychosocial interviews specifically for chronic pain. Three Virtual Human interview scripts will be developed: One that facilitates participant disclosure of psychological distress, coping, medication usage, and stressful live events; one that mirrors this condition but includes explanations of how the mind contributes to chronic pain, and a control condition that asks about participants' medical history, medications, and chronic pain background. Adult patients who experience chronic musculoskeletal pain, are fluent in English, have no visual and cognitive impairment that would interfere with participation, have an average pain score of 4 or higher during the past week on a 0 to 10-point scale, and are receiving treatment for their chronic pain will be recruited through flyers from the Keck Medical School and invited to participate in a session with a Virtual Human at USC's Institute for Creative Technologies (ICT). Each patient who agrees to participate will come to ICT and will be assigned to one of the three VH conditions. The session at ICT consists of written informed consent followed by online questionnaires (e.g., demographics, mental and physical health, stressful live events, pain medication usage, coping), followed by the VH session, followed by post-session online questionnaires (e.g., satisfaction with the VH session), and then a brief structured interview with a research assistant about patients' experience with the VH. Patients will also be invited to participate in a brief online survey one month after the session with the VH at ICT. Patients will be compensated \$70 via Amazon gift card for the 1 1/2 to 2 hour session at ICT and an additional \$10 via Amazon gift card, if they agree to complete the online survey about one month after the study visit at ICT. Based on participant feedback (qualitative and quantitative), the Virtual Human interviews will be refined as necessary to improve the sessions.

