The goal of this project is to develop three Virtual Human (VH) interview conditions for patients who experience chronic pain. Two of these VH conditions will focus on participants' disclosure of negative mood, psychological distress, coping with chronic pain, stressful life experiences, pain medication usage, and personality characteristics. The third condition is a control condition that focuses on the medical aspects of patients' chronic pain experience including their pain medication usage. In order to develop the best possible VH interviews, stakeholder feedback by patients is critical. We will, therefore, pilot test the three VH interviews with patients who experience chronic pain to get their qualitative (e.g., structured interview) and quantitative feedback (e.g., questionnaires) about their experience and how the VH interviews could be improved. In order to examine the best features of a Virtual Human coach, we will compare Virtual Humans that deliver the session either with a computer-generated voice or a voice recorded by a real person. Half of the patients in each of the three conditions will hear the computer-generated Virtual Human voice and the other half will hear the voice recorded by a real person. Patient feedback will tell us whether patients might prefer one Virtual Human voice over the other.

Chronic pain is accompanied by a host of emotional, behavioral, and cognitive psychosocial consequences. At the same time, psychosocial factors contribute to chronic pain, including fear of movement and catastrophizing, maladaptive emotional and cognitive processes, and adverse life experiences. Treatment guidelines stress the importance of psychosocial aspects in pain management. Unfortunately, both patients and medical providers find it difficult to discuss psychosocial problems. The goal of this project is to remedy this critical problem by developing and pilot testing novel therapeutic interviews delivered by next-generation

Virtual Humans (VHs) to help patients engage in discussions about pain-related psychosocial factors.

Provide a summary of the background of the study and explain how this research will contribute to existing knowledge. Describe previous work that provides a basis to show that the proposed research can be carried out without undue risk to human subjects. Include relevant citations.

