- 1) We will ask patients to complete different questionnaires pertaining to their demographics and medical background, their emotions, chronic pain management and medication usage, and stressful events. These questionnaires will be completed in an online survey before and after the interview with a Virtual Human and in the brief online survey about a month after the visit at ICT for the study.
- 2) Patients will also be asked to interact with a Virtual Human interviewer. This study has three different types of interviews, and patients will be assigned to one of them. In the course of this interaction, they will be asked to answer personal questions, such as about their emotions, stressful life experiences, how they cope with chronic pain, and their medical treatment and pain medication usage for chronic pain. The Virtual Human interview will be audio-recorded for analysis purposes.
- 3) At the end of the ICT study visit, we will ask patients to tell us about their experiences with the Virtual Human in a structured interview with our research staff. The goal of this interview is to learn how they felt about their interaction with the Virtual Human and if we can improve the interviews. This interview with research staff will also be audio-recorded for analysis purposes.

If patients do not want to be audio-recorded, they cannot participate in this research study.

Describe the statistical considerations for the study, how the sample size was determined, and how the results will be analyzed, if applicable.

Pilot studies typically consist of relatively small sample sizes and our proposed study sample consists of 35 to 50 patients. Given that this study will iteratively refine the Virtual Human interview scripts depending upon participant feedback, we will recruit up to 50 participants, if the Virtual Human scripts more need refinement. Patient feedback will be in the form of qualitative (e.g., a brief structured interview with a research assistant at ICT) and quantitative (e.g., standard questionnaires) data. These data will inform us whether the Virtual Human interview scripts function as intended, need improvement, and whether participants enjoyed the interaction with the Virtual Human. The majority of patients will be assigned to the two psychosocial Virtual Human conditions and fewer to the control condition.

Deception

Describe why the research cannot be carried out without deception.

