Official Grant Title: Virtual Human Technology for Patients with Chronic Pain

Working Title: Virtual Human–Delivered Interviews for Patients with Chronic Pain: Feasibility, Acceptability, and a Pilot Randomized Trial of Standard Medical, Psychosocial, and Educational Interviews

NCT #: 04349033

Date: October 15, 2021

Statistical Analysis Plan

To test our aim (whether interviews affected pain-related outcomes about one month later), we will conduct intent-to-treat (ITT) analyses using data from all patients, accommodating missing values on outcomes using maximum likelihood parameter estimation. Two-way repeated-measures ANOVAs with one between-subjects factor (experimental condition) and one within-subject factor (time) will be tested using linear mixed effects models (using the MIXED procedure in SAS 9.4; Cary, NC). Analyses will focus on time by group interactions (indicating group differences in change from baseline) for two specific comparisons: 1) Psychosocial vs. Standard; and 2) Educational vs. Standard. We will also inspect changes from baseline within each of the three experimental conditions separately using post-hoc contrasts. We will include VH voice (human vs. computer) as a covariate in all models and include age and education as covariates in sensitivity analyses.

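### Age and education enter without a time interaction, so the planned sensitivity analysis cannot correct a difference in change for imbalance in them; the voice term has the same gap, for precision only

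*SAP*

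**What the plan says.** The SAP fits a linear mixed model with condition, time and their interaction. Baseline is one of the responses, not a covariate. The target is explicit: "Analyses will focus on time by group interactions (indicating group differences in change from baseline) for two specific comparisons", namely each of the two active interviews against Standard. Within-condition changes are also examined. Missing data are handled by "accommodating missing values on outcomes using maximum likelihood parameter estimation".

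On covariates there is one sentence: "We will include VH voice (human vs. computer) as a covariate in all models and include age and education as covariates in sensitivity analyses". Group by time is the only interaction that either document names, and no analysis with baseline as a covariate is planned.

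Three points in the protocol bear on this:

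- On allocation (Methods and Procedures, statistical considerations): "The majority of patients will be assigned to the two psychosocial Virtual Human conditions and fewer to the control condition". The total is 35 to 50 and no ratio is given.
- On voice (Research Objectives and Background): "Half of the patients in each of the three conditions will hear the computer-generated Virtual Human voice", with the rest hearing a recorded human voice.
- On timing (opening summary), consent is "followed by online questionnaires (e.g., demographics, mental and physical health, stressful live events, pain medication usage, coping), followed by the VH session". Voice therefore cannot affect the baseline values.

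**The concern.** The quantity tested is a difference in change, but age, education and voice are constant within a patient. Entered as main effects, they adjust the level of the outcome and not its change. If the arms differ by chance in age or education, and these predict how much a patient changes, the imbalance passes straight into the contrast. The planned model does not remove it.

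This is the only covariate sensitivity analysis in the SAP. A reader who sees that adjusting for age and education left the result unchanged would take that as evidence of robustness. With complete data, the agreement is forced by the algebra.

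For voice the form is also wrong, since voice can act only after baseline. The even split within conditions means the group contrast loses precision at most.

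**Working it through.** The plan gives no figure to reproduce: no effect size, SD, correlation, dropout rate or allocation ratio is stated, and the sample size is not derived from a formula.

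**Assumed inputs.** Arms (Standard/other/other) 10/20/20 or 7/14/14. Outcome SD 1 and baseline to one-month correlation 0.5, so the residual variance of change is 1 + 1 − 2 × 0.5 = 1. Standardized age and education each have slope 0.3 on baseline and 0 or 0.3 SD on change. One-month values are missing at random in 0, 20 or 30%.

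**Step 1: algebra.** Let Y(i,t) = μ(g,t) + βx(i) + e(i,t), with x fixed within patient i. Then Y(i,1) − Y(i,0) = μ(g,1) − μ(g,0) + e(i,1) − e(i,0), and βx has gone. With complete data, the group-by-time contrast is the least-squares contrast of change on group, whether or not x is in the model. This holds under compound symmetry. It also holds under unstructured covariance, because the regressors for change are nested in those for level. It depends on none of the assumed values.

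**Step 2: likely imbalance.** The SD of the Standard-versus-other difference in a standardized covariate mean is √(1/10 + 1/20) = 0.387 or √(1/7 + 1/14) = 0.463. A gap above 0.3 SD then has probability 44% (0.3/0.387 = 0.78) to 52% (0.3/0.463 = 0.65) per covariate and contrast.

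**Step 3: complete data, by simulation.**

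- Main effects shift the contrast by at most 3 × 10⁻¹⁴ SE, with SE ratio 1.000.
- Crossed with time, slope on change 0.3: mean shift 0.33–0.34 SE, and the SE falls 5–6%. As a rough check, two independent imbalances give a shift with SD √2 × 0.3/√(1 + 2 × 0.3²) = 0.424/1.086 = 0.39 SE. The mean absolute shift is then 0.80 × 0.39 = 0.31 SE, before the noise of estimating the slopes.
- Crossed with time, slope on change 0: mean shift 0.15–0.19 SE (noise), and the SE rises 2–3%.

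**Step 4: missing one-month values, maximum likelihood, unstructured covariance.** Main effects now move the estimate by a mean of 0.08–0.16 SE (95th percentile 0.23–0.43, largest 1.3), through patients who lack the one-month value. The question is whether that movement removes the imbalance. The table gives the slope of the estimated contrast on the age-plus-education imbalance (true value 0.3; 244–250 simulated trials per row).

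| Arms | Missing | Neither covariate | Main effects | Crossed with time |
|---|---|---|---|---|
| 10/20/20 | 20% | 0.268 | 0.270 | −0.022 |
| 10/20/20 | 30% | 0.238 | 0.243 | −0.041 |
| 7/14/14 | 20% | 0.331 | 0.328 | 0.050 |
| 7/14/14 | 30% | 0.366 | 0.359 | 0.017 |

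Main effects leave the dependence where it was. Crossing with time removes it.

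**Step 5: different assumptions.** Here there is one covariate, correlation 0.6, an imposed imbalance of 0.5 SD and a slope on change of 0.4, so the expected bias is 0.5 × 0.4 = 0.20 SD. At 10/20/20 with unstructured covariance and 300 trials, the mean estimates (true effect 0) were:

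| Missing | No covariate | Main effect | Crossed with time |
|---|---|---|---|
| 0% | 0.226 | 0.226 | 0.035 |
| 20% | 0.200 | 0.197 | −0.008 |

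**Step 6: voice.** With an even split, an omitted voice effect d on change adds 0.25d² to the variance of change. The SE saved by including voice × time is 1 − 1/√(1 + 0.25d²). That is 3.0% at d = 0.5, 0.5% at d = 0.2, and nothing at d = 0. With complete data and even arm sizes the estimate does not move.

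**The case against.** The strongest reply is that the SAP does not exclude covariate-by-time terms and does not say what the sensitivity analysis is for. Both are true. The finding rests on the ordinary reading of a sentence that adds covariates and names no interaction for them. If the terms were intended, the sentence still has to say so.

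A second reply is that main effects have a use under maximum likelihood. If dropout depends on age or education, including them makes missing at random more plausible. Under assumed values (slope 0.3 on level, correlation 0.5, about 27–30% dropout that depends on age differently across arms), leaving them out biases the contrast by about 0.04–0.07 SD, and a main-effects model removes that. So the planned model is not empty when data are missing. The crossed model gives the same protection and also deals with imbalance that affects change.

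Third, imbalance comes mainly from the small total and not from the smaller control arm: equal arms would still give an SD of √(2/16.7) = 0.35 at 50 patients or √(2/11.7) = 0.41 at 35. This is right, and unequal allocation only adds to it. A large gap is also less common: above 0.5 SD has probability about 20–28%.

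Fourth, slopes of 0.3 are generous. Together they explain 0.18/1.18 = 15% of the variance in change, and the documents give no basis for that. At slope 0.1 the crossed model shifts the contrast by 0.18–0.21 SE, little more than noise, with an SE 1–2% larger; precision improves only from slopes of roughly 0.15–0.2. That limits the size of the benefit. It does not give the main-effects model any ability to correct change.

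**Conclusion.** The concern holds. As written, the age and education analysis leaves both contrasts, their SEs and the within-condition changes exactly as they were when follow-up is complete. When one-month values are missing it moves the estimate without removing the effect of imbalance on change. The complete-data result is algebra and rests only on the main-effects reading. The other sizes rest on the assumed arms, correlation, slopes and dropout: if the slopes on change are 0.3, a working adjustment would shift the contrast by about a third of an SE on average; if they are near zero, there is little to correct.

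For voice the loss is precision only, 0–3% of the SE for effects up to 0.5 SD, provided the even split is kept. The main contrast stays valid under randomization and no inflation of type I error is claimed. This is a weakness in a sensitivity analysis. It should be fixed because agreement would otherwise be misread as robustness.

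**What to change.** Replace the covariate sentence in the SAP with:

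> All models will include voice and voice × time. Sensitivity analyses will add age, age × time, education and education × time, with covariates centred at the overall sample mean, in the same all-patients maximum likelihood mixed model.

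Centring keeps the within-condition changes interpretable as changes at average age and education. State also how education is coded.

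The cost is one sentence, one error degree of freedom for each added time interaction (more if education is categorical), and an SE about 2–3% larger in the sensitivity analysis if age and education do not predict change. Adding voice × time does alter the main model. With even arms and complete data it leaves the estimate unchanged.
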